12.1.3 Allocation of TEAEs to Treatment Periods

TEAEs will be allocated to treatment periods according to the time of onset of the adverse event:

- *TEAE in the Placebo-controlled Period* – a TEAE that starts before the date and time of the start of Visit 5 IMP infusion, or, for the participants with no Visit 5 IMP infusion, a TEAE that starts before Week 12.
- *TEAE in the Open-label Period* – a TEAE that starts, increases in intensity or becomes serious during or after administration of Visit 5 IMP infusion.

This implies that for participants in the APTS-FU, adverse events reported after withdrawal in the Placebo-controlled Period but before Week 12, will be allocated to the Placebo-controlled Period.

For allocation of TEAEs to treatment periods, the same rule for imputed dates as specified in Section 15.14.3 applies, i.e. for incomplete start dates, only the imputed start date and not the time (which will not be imputed) of the adverse event will be taken into account in the allocation of the TEAE to periods.

If an adverse event starts on the day of the Visit 5 IMP infusion, but with an unknown start time, the adverse event will be classified as treatment-emergent in the Placebo-controlled Period.

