12.1 Adverse Events

12.1.1 General Methodology for Adverse Events

Unless otherwise specified, tables, graphs, and listings will be based on the APTS for the Placebo-controlled Period and the APTS-OL for the Open-label Period.

All the tables and graphs will be presented by treatment group for the Placebo-controlled Period and by treatment sequence group for the Open-label Period, unless otherwise specified.

Tables by preferred term and tables by SOC and preferred term will be sorted in descending order based on the percentages of participants with these adverse events in EPTI-EPTI or PBO-EPTI group.

Unless otherwise specified, the summaries of adverse events will include the number and percentage of participants with an adverse event. In tables displaying SOC or preferred terms, participants are counted only once within each SOC or preferred term.

Listings of adverse events will be sorted by treatment group including participant ID with site ID, Age, Sex, Race, AE number, SOC/PT/investigator term, AE start date/time, AE stop date/time/ongoing, date of first IMP infusion, date of the latest IMP infusion prior to the adverse event, time since latest IMP infusion, duration of the adverse event, frequency type (continuous/Intermittent), intensity, seriousness, relationship to IMP (Probable/Possible/Not Related: Specify), action taken with IMP and outcome. For adverse events that change in intensity, each intensity will be included. In listings of adverse events, start or stop dates will be displayed as collected also in case of partially or completely missing dates.

All adverse events will be coded using MedDRA, Version 25.0 or later.

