12.1.2 Classification of Adverse Events

Adverse events will be classified according to the time of onset of the adverse event:

pre-treatment adverse event – an adverse event that starts on or after the date the participant signed the *Informed Consent Form* and prior to the date and time of first dose of IMP

treatment-emergent adverse event (TEAE) – an adverse event that starts during or after administration of the first dose of IMP, or a pre-treatment adverse event that increases in intensity or becomes serious during or after administration of the first dose of IMP

For handling of adverse events with incomplete start dates to facilitate this classification, see Section 15.14.3. Note that adverse events with incomplete start dates will be classified as treatment-emergent simply if the imputed start date is on or after the date of first IMP infusion, since the start time of the adverse event will not be imputed, unless the investigator in such a case has assessed that the causality to IMP is “Not Related - Prior to IMP”.

An adverse event is considered causally related to the use of the IMP when the causality assessment by the investigator is probable or possible. If the causality assessment is missing, the adverse event is considered causally related.

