12.1.5 Treatment-emergent Adverse Events

The following summaries will be provided by treatment group for the Placebo-controlled Period and by treatment sequence for the Open-label Period:

- TEAEs by SOC and preferred term
- TEAEs with an incidence $\geq 2\%$ in any treatment group by preferred term
- causally related TEAEs by SOC and preferred term
- TEAEs by intensity (*mild/moderate/severe*), SOC, and preferred term
- causally related TEAEs by intensity, SOC, and preferred term
- TEAEs occurring on the day of dosing after infusion start by SOC and preferred term (this includes day of Visit 2 infusion for the Placebo-controlled Period and day of Visit 5 infusion for the Open-label Period)

The summaries will be provided for the APTS for the Placebo-controlled Period and for APTS-OL for the Open-label Period.

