12.1.6 Serious Adverse Events

Treatment-emergent SAEs will be summarized by treatment group for the Placebo-controlled Period based on APTS and by treatment sequence for the Open-label Period based on APTS-OL by:

- SOC and preferred term

All SAEs occurring before entering the Open-label Period will be listed for the APRS.

All SAEs occurring at or after entering the Open-label Period will be listed for the APTS-OL.

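### SAP 12.1.3 counts a pre-treatment adverse event that first worsens or becomes serious after the Visit 5 infusion as a Placebo-controlled TEAE, because that period's rule looks only at the start date

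*SAP*

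**What the plan says.** SAP 12.1.2 gives two routes to TEAE status. One is onset during or after the first infusion. The other is "a pre-treatment adverse event that increases in intensity or becomes serious during or after administration of the first dose of IMP". The second route has no end date, so worsening after Visit 5 satisfies it.

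SAP 12.1.3 then assigns TEAEs to periods. Its lead-in says "TEAEs will be allocated to treatment periods according to the time of onset of the adverse event". The two bullets differ in form:

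- Placebo-controlled Period: "a TEAE that starts before the date and time of the start of Visit 5 IMP infusion". For participants without a Visit 5 infusion, the limit is a start before Week 12.
- Open-label Period: "a TEAE that starts, increases in intensity or becomes serious during or after administration of Visit 5 IMP infusion".

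The period tables rest on this allocation. SAP 12.1.6 states that "Treatment-emergent SAEs will be summarized by treatment group for the Placebo-controlled Period based on APTS", and SAP 12.1.5 lists "TEAEs by intensity" for each period. Neither section says whether intensity and seriousness in the Placebo-controlled tables are those reached before Visit 5 or over the whole life of the event. For listings only, SAP 12.1.1 says "For adverse events that change in intensity, each intensity will be included".

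Protocol 16.9.1 leaves the allocation of TEAEs to periods to the SAP, so the protocol does not settle the matter.

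**The concern.** The Placebo-controlled Period is the trial's only randomised safety comparison; after Visit 5 every infused participant receives eptinezumab. A TEAE table for that period should contain only what emerged between the first infusion and Visit 5. A rule based on start date alone also admits events that began before any treatment, did not change while the arms differed, and changed only later.

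The raw material for such events is collected. Protocol Panel 2 has signs and symptoms at Screening and Baseline entered on the Adverse Event Form, and Protocol 10.1.1 requires pre-treatment events to be recorded.

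The stake is a false entry in a randomised safety table, in either arm. A second, lesser stake is that two programmers could tabulate the grade or seriousness of an event that began before Visit 5 differently, because no cut is stated.

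**Working it through.** The plan gives no figure to reproduce, so the check is to run event histories through the rules as written.

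**Inputs.** First infusion on day 0 and Visit 5 on nominal day 84 (SAP 15.13.3, Table 11). TEAE definition from SAP 12.1.2; period rules from SAP 12.1.3. The event days below are illustrative.

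**Rules.** Let s be the start day and w the day the event worsens or becomes serious, if it does.

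- TEAE: s ≥ 0, or w ≥ 0.
- Placebo-controlled (PC) as written: TEAE and s < 84.
- Open-label (OL) as written: TEAE and (s ≥ 84 or w ≥ 84).
- PC as proposed under the fix: 0 ≤ s < 84, or (s < 0 and 0 ≤ w < 84).

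| History | s | w | PC as written | OL as written | PC as proposed |
|---|---|---|---|---|---|
| (a) starts after first dose, no change | 30 | – | yes | no | yes |
| (b) starts after first dose, worsens before Visit 5 | 30 | 60 | yes | no | yes |
| (c) starts after first dose, worsens or becomes serious after Visit 5 | 30 | 90 | yes | yes | yes |
| (d) pre-treatment, worsens before Visit 5 | −10 | 30 | yes | no | yes |
| (e) pre-treatment, first worsens or becomes serious after Visit 5 | −10 | 90 | **yes** | yes | **no** |
| (f) pre-treatment, no change | −10 | – | no | no | no |
| (g) starts after Visit 5 | 90 | – | no | yes | no |

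**Reading the table.** Only (e) is wrong as written: nothing emerged between day 0 and day 84, yet the event enters the PC table. It is also in the OL table, where it belongs. In (c) the PC entry is right, because the event began on randomised treatment. What is undefined in (c) is whether the PC tables show the grade and seriousness from before or after day 84. The proposed rule changes (e) and nothing else.

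**No Visit 5 infusion.** The PC limit becomes Week 12 and the OL rule cannot be met. A history like (e), with worsening after Week 12, is then allocated to the PC period only. The separate APTS-FU listing in SAP 12.1.4 requires a start date after Week 12, so the event does not qualify for it.

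**Size per event.** On the planned 285 per arm, and assuming all are treated, one affected participant adds 1/285 = 0.0035, or 0.35 percentage points, to that arm's incidence. SAP 12.1.1 counts a participant once per system organ class or preferred term, so the addition is zero at any level where the participant already has a PC TEAE.

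**The case against.** The best defence has four parts.

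- **The Open-label bullet already captures later worsening.** This is true, and it matters. A reader might infer that open-label events are moved to placebo and lost from the open-label tables. They are not: where Visit 5 was infused, the event is counted in both periods. A correct second entry does not, however, remove the false first one.
- **The word for start could be meant as emergence.** The lead-in on time of onset gives this some colour. But the Open-label bullet names starting, worsening and becoming serious as three separate triggers, so starting cannot sensibly cover all three in the bullet above it.
- **The Placebo-controlled database is locked separately.** SAP section 4 plans that lock, followed by analysis of data collected in that period. This may keep some later updates out in practice, but it does not state an event-level cut for an ongoing event whose record is updated after Visit 5. Conversely, a reader might infer that the Placebo-controlled tables would change between the two locks. The documents do not say these tables are rerun, and the second classification covers only APTS-OL and APTS-FU.
- **Events that start before Visit 5 and become severe or serious later are properly Placebo-controlled TEAEs.** This stands. A reader might infer that they will be tabulated as serious or severe on placebo. The SAP does not prescribe that; it is silent. Listings show each intensity, and changes of intensity carry their own dates.

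A reader might also infer that the rule inflates the placebo rate in particular and dilutes the comparison. It applies to both arms. Visit 5 is the placebo arm's first eptinezumab infusion, and Protocol 1.1.3 reports fatigue as most frequent on the day of the first infusion, so an imbalance is possible. No document gives rates from which its direction or size could be derived.

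**Conclusion.** The point holds in a narrow form. Read literally, SAP 12.1.2 and 12.1.3 together place one kind of event wrongly in the randomised safety tables: a pre-treatment event that first worsens or becomes serious after Visit 5, or after Week 12 without a Visit 5 infusion. It affects whichever arm the participant was randomised to. Where Visit 5 was infused, it is a double count and not a transfer. For events that begin between the first dose and Visit 5, the fault is only an unstated cut for grade and seriousness.

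The frequency cannot be derived from the documents, so neither a number of affected participants per arm nor an effect on a risk ratio can be supported. The SAP plans counts and percentages for adverse events, not risk ratios. The effect may be small, since it needs a pre-treatment event that first changes only after Visit 5.

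The wording should still be changed, because a stated rule yields a wrong entry in the only randomised safety comparison and the correction is simple. The conclusion rests on the literal text; programming specifications outside these documents might already apply the intended cut.

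**What to change.** Replace the first bullet of SAP 12.1.3 with wording to this effect: *a TEAE belongs to the Placebo-controlled Period if the event began at or after the start of the first IMP infusion, or began earlier and then worsened or turned serious during or after that infusion, in either case ahead of the start of the Visit 5 infusion (or ahead of Week 12 where Visit 5 was not infused).*

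Add one sentence for SAP 12.1.4 to 12.1.6: *Placebo-controlled tables use the worst intensity, and the seriousness, reached before that cut.* The Open-label bullet and the rule for an unknown start time on the day of Visit 5 can stay as they are.

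One consequence needs settling. For participants without a Visit 5 infusion, a pre-treatment event that first worsens after Week 12 would leave the Placebo-controlled tables and still not qualify for the APTS-FU listing. Extending that listing to worsening after Week 12 would cover it.

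The cost is SAP text and programming. Changes of intensity are recorded on the Adverse Event Intensity Log (Protocol 10.4), and SAP 15.14.3 handles incomplete dates. The documents do not show that the date an event became serious is captured separately, so the sponsor must confirm its source before the seriousness cut can be programmed.

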6.1 Treatment Regimen

Patients will be randomly allocated via a centralized randomization system to one of two treatment groups: eptinezumab 100 mg, or placebo, in a ratio of 1:1.

The patient will receive IMP at the Baseline Visit with either eptinezumab or placebo by intravenous infusion.

At the Visit 5 all patients who were assigned to either eptinezumab or placebo will enter the open-label period and receive an intravenous infusion with eptinezumab 100 mg.

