10.4 Recording Adverse Events

Adverse events (including pre-treatment adverse events) must be recorded on an *Adverse Event Form*. The investigator must provide information on the adverse event, preferably with a diagnosis, or at least with signs and symptoms; start and stop dates (and start and stop time if the adverse event lasts less than 24 hours); intensity; causal relationship to the IMP; action taken; and outcome. If the adverse event is not related to the IMP, an alternative aetiology must be recorded, if available. If the adverse event is an overdose, the nature of the overdose must be stated (for example, medication error, accidental overdose, or intentional overdose). If the intensity changes during the course of the adverse event, this must be recorded on the *Adverse Event Intensity Log*.

If the adverse event is *serious*, this must be indicated on the *Adverse Event Form*. Furthermore, the investigator must fill out a *Serious Adverse Event Form* and report the SAE to H. Lundbeck A/S immediately (within 24 hours) after becoming aware of it (see section 10.5).

If individual adverse events are later linked to a specific diagnosis, the diagnosis should be reported and linked to the previously reported adverse events.

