8.1 Recent and Concomitant Medications

Recent and concomitant medication is any medication other than the IMP that is taken during the trial, up until the Safety Follow-up Contact, including during the screening period. Recent and concomitant medication will be coded using the *WHO Drug Dictionary Enhanced* (WHO-DDE).

Medications will be classified according to the start and stop dates and summarized by anatomical therapeutic chemical (ATC), generic drug name and treatment group. Handling of missing or incomplete dates is specified in Section 15.14.4.

The following categories will be used:

- Prior medications: Medications taken prior to the first IMP infusion.
- Concomitant medications taken during the Placebo-controlled Period: Medications with a start date prior to Visit 5 and an end date that is either missing or at or after the date of first IMP infusion, medications with a missing start date and an end date at or after the date of first IMP infusion, and medications missing both stop and start dates. For participants in the APTS-FU set, concomitant medications reported after withdrawal in the Placebo-controlled Period but before Week 12, will be allocated to the Placebo-controlled Period, see also Section 3.2.
- Concomitant medications during the Open-label Period: Medications with a start or stop date at or after the date of visit 5 IMP infusion and medications where both start and stop date are completely missing. Ongoing medications are also included, as well as medications with a completely missing stop date.
- Concomitant medications reported in connection to the Safety Follow-up visit (applicable only for the APTS-FU analysis set if information on any such medications have been collected): Medications with a start or stop date at or after Week 12.

The tables for prior medication, concomitant medications during the Placebo-controlled Period will be based on APTS, and concomitant medications during the Open-label Period will be based on the APTS-OL. The prior and concomitant listing will be provided with an identified variable to show whether the medication is prior, concomitant during the Placebo-controlled Period, or concomitant during the Open-label Period.

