15.14.3 Adverse Event Start and Stop Dates

Imputation of partially or completely missing dates will be included in data in order to document the classification of the treatment emergent status. For an adverse event with an imputed start date, the classification of treatment emergent will depend only on whether the imputed date is the same as the date(s) of infusion and not the timepoint of the infusion, since start times for adverse events will not be imputed. No duration will be calculated for adverse events with incomplete start-or-stop dates or for ongoing adverse events.

Imputation will follow the algorithm below. If an imputed start date after this procedure is after the end date, the start date will be set to the end date.

Start Dates

Participants with no IMP infusion

For participants who have not been treated, the imputation of AE start date will be performed as follows, where UK and UKN indicate unknown or missing day and month, respectively:

- UK-MMM-YYYY: The start date will be imputed with either the 1st of the month, or date of Visit 1. Date of Visit 1 will be used if that is the later of the two and if it is within the specified month and year
- UK-UKN-YYYY: The start date will be imputed with either JAN 1, or date of Visit 1. Date of Visit 1 will be used if it is within the specified year

If the AE start date is completely missing, it will be set equal to the date of Visit 1.

Patients who received IMP infusion

For participants, who have been treated, the imputation of AE start dates will be performed as follows:

- **UK-MMM-YYYY:**
 - If the year and month are equal to the year and month of treatment start date, the adverse event start date is imputed with the date of IMP dose
 - If the year is equal to the year of treatment start date: If the month is prior to the treatment start date, the adverse event start date is imputed with the last day of the month. If the month is equal to the month of the treatment start date, see above. If the month is after the month of the treatment start date, the adverse event start date is imputed with the first day of the month
 - If the year is prior to treatment start date, the adverse event start date is imputed with the last day of the month
 - If the year is after the year of treatment start date, the adverse event start date is imputed with the first day of the month
- **UK-UKN-YYYY:**

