15.14.4 Medication Start and Stop Dates

Imputation of incomplete or partially missing dates will be performed in order to document the assigned categories specified in Section 8.

The algorithm for imputing the start dates will follow the one used for imputing adverse event start dates, see Section 15.14.3.

For imputing stop dates, the following will apply, where UK and UKN indicate unknown or missing day and month, respectively:

- **UK-MMM-YYYY:** Medication end date is imputed with the last day of the month

- UK-UKN-YYYY: Medication end date is imputed with 31-DEC-YYYY

Medications marked as ongoing are considered concomitant medications in one or both of the periods (Placebo-controlled Period and Open-label Period), depending on the (possibly imputed) start date, i.e. if the start date is at or after the date of Visit 5 IMP infusion, the medication is only considered ongoing in the Open-label Period.

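### Adverse events with no start time on the Visit 5 infusion day default to the Placebo-controlled Period, so a reaction of 24 hours or more to open-label eptinezumab can be counted under placebo

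*SAP*

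**What the plan says.** - **Allocation rule.** SAP 12.1.3 allocates treatment-emergent adverse events (TEAEs) to periods by onset relative to the start of the Visit 5 infusion. The Open-label category is "a TEAE that starts, increases in intensity or becomes serious during or after administration of Visit 5 IMP infusion". The section ends with a rule for an event that starts on the day of that infusion "but with an unknown start time, the adverse event will be classified as treatment-emergent in the Placebo-controlled Period". It states no exception for causality or any other evidence of when the event began.
- **When a time is recorded.** Protocol 10.4 requires "start and stop dates (and start and stop time if the adverse event lasts less than 24 hours"). For longer events only dates are required. SAP 15.14.3 leaves a missing time missing, "since start times for adverse events will not be imputed".
- **What is infused at Visit 5.** Under Protocol 6.1, all participants, whichever arm they were randomised to, "will enter the open-label period and receive an intravenous infusion with eptinezumab 100 mg".
- **How tables are laid out.** Under SAP 12.1.1, Placebo-controlled tables are by treatment group (PBO, EPTI) and Open-label tables by treatment sequence (PBO-EPTI, EPTI-EPTI).
- **The default at the first infusion.** SAP 12.1.2 covers adverse events with incomplete start dates. Such an event "will be classified as treatment-emergent simply if the imputed start date is on or after the date of first IMP infusion", unless the investigator has assessed it as unrelated because it preceded the IMP.

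**The concern.** Events of 24 hours or more can lack a start time without any breach of the protocol, so the tie-break will be used in ordinary conduct. When it is used, the event goes to the period before the eptinezumab infusion. For a placebo-arm participant, a reaction to a first dose of eptinezumab then appears in the PBO column of the Placebo-controlled tables.

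This reaches more than the overall TEAE table. An event that the investigator judged probably or possibly related would appear as causally related under PBO (SAP 12.1.5). The hypersensitivity and anaphylaxis category in SAP Table 15 has no timing condition, so such an event would also enter the PBO column of the adverse-events-of-special-interest tables. The Open-label tables would be short by the same events. At stake is the descriptive safety comparison and the description of reactions to the second infusion visit, not any efficacy result.

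**Working it through.** The plan states no figure for this point. The check applies the rules to each case and then illustrates the size.

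**1. Adverse events with onset on the Visit 5 day (SAP 12.1.3)**

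| True onset | Start time | Later worsens or becomes serious | Period |
|---|---|---|---|
| After infusion start | Recorded | Either | Open-label |
| Before infusion start | Recorded | No | Placebo-controlled |
| Before infusion start | Recorded | Yes | Both |
| Before or after | Unknown | No | Placebo-controlled only |
| Before or after | Unknown | Yes | Both |

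The problem lies in the fourth row, where true onset was after infusion start.

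**2. Size per participant.** The planned arm size is 285 (Protocol 16.12). One participant is 1/285 = 0.35 percentage points. For the table of terms with incidence of at least 2% in any group, the threshold is 0.02 × 285 = 5.7, that is 6 participants, so a few events can decide whether a term appears.

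**3. Illustration, equal frequency in both arms.** Protocol 1.1.3 gives hypersensitivity reactions as 3% on 100 mg and 1% on placebo, from studies with two infusions. On 285 these are 8.55 and 2.85 participants. Let k participants per arm be affected; k is an assumption with no source.

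PBO = (2.85 + k)/285; EPTI = (8.55 + k)/285.

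| k | PBO | EPTI | Difference (points) | Ratio |
|---|---|---|---|---|
| 0 | 1.00% | 3.00% | 2.00 | 3.00 |
| 1 | 1.35% | 3.35% | 2.00 | 2.48 |
| 2 | 1.70% | 3.70% | 2.00 | 2.18 |
| 3 | 2.05% | 4.05% | 2.00 | 1.97 |

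The difference holds; the PBO rate and the ratio do not. k = 3 is demanding: it equals 3/8.55 = 35% of the count implied by the 3% rate.

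**4. Illustration, unequal frequency.** Protocol 1.1.3 gives fatigue as about 3% on eptinezumab and 2% on placebo. It was most frequent on the day of the first infusion and comparable to placebo with later ones. Visit 5 is the first eptinezumab infusion for the placebo arm and the second for the other arm. The excess is 3% − 2% = 1 point, or 0.01 × 285 = 2.85 participants. Let s be the share of that excess that began on the infusion day, lasted 24 hours or more and had no recorded time. EPTI is held at 3%, because the excess is taken to be absent at a second infusion.

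PBO = (5.70 + 2.85s)/285.

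| s | PBO | Difference (points) |
|---|---|---|
| 0% | 2.0% | 1.0 |
| 10% | 2.1% | 0.9 |
| 50% | 2.5% | 0.5 |
| 100% | 3.0% | 0.0 |

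The last row is a mathematical ceiling, not an expectation. The protocol describes the raised incidence as lasting through the first week, so not all of the excess falls on the infusion day.

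Both illustrations assume that all 285 per arm are dosed at Visit 5. They ignore participants who already had the same term earlier in the period, who are counted once. Both simplifications overstate the effect.

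**The case against.** **It is a prespecified convention.** Protocol 16.9.1 leaves period allocation to the SAP, the SAP states a rule, and with an unknown time either default misplaces some events. This stands. A reader might infer that 12.1.3 contradicts itself, because its Open-label definition covers events that start after the infusion. It does not: the last sentence is an explicit rule for the case that the definition cannot settle. The criticism is of the rule's direction.

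**Few events may be untimed.** Protocol 10.4 is a minimum, the listings carry a start date/time field (SAP 12.1.1), and sites check adverse events before, during and after the Visit 5 infusion (Protocol 8.5). The protocol adds that most hypersensitivity reactions occurred during infusion, where sites are likely to note a time. This stands, and it is why the number is probably small.

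**The events can be traced.** Listings show start date/time, latest infusion date, causality and actual treatment sequence. This stands, but the tracing is by hand, and SAP version 3.0 dropped the infusion-reaction column from the adverse event listings.

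**The day-of-dosing summary.** A reader might infer that 12.1.3 removes these events from the Visit 5 day-of-dosing summary in SAP 12.1.5. That does not follow: the summary requires onset after infusion start, which an untimed event cannot show under either allocation.

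**Comparison with other defaults.** For medications, SAP 8.1 puts in the Open-label Period "Medications with a start or stop date at or after the date of visit 5 IMP infusion", and for an ongoing one started on that date SAP 15.14.4 says "the medication is only considered ongoing in the Open-label Period". A reader might call this an inconsistency. It is weak support: those rules work on dates alone, and the documents plan no table that links medications to adverse events. SAP 12.1.2 is closer but also only supporting, because it concerns incomplete dates and whether an event is treatment-emergent at all.

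**Conclusion.** The point holds as a minor one. Applied as written, SAP 12.1.3 can place an eptinezumab reaction in the PBO column, including one judged causally related or a hypersensitivity event of special interest. The same event is then missing from the Open-label tables unless it later increases in intensity or becomes serious. The first-infusion rule in SAP 12.1.2, by contrast, leans toward exposure and lets the investigator override it; Visit 5 has neither feature.

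The size cannot be derived from the documents. Each affected participant is about 0.35 points of 285, and the tables in the working rest wholly on assumed counts and shares.

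A reader might infer that the rule biases the comparison between arms toward no difference. The documents do not support that in general. Both arms receive eptinezumab at Visit 5, so with equal frequency both columns rise and the difference hardly moves, although the PBO rate and the ratio are distorted. An unequal effect needs reactions that are commoner at a first eptinezumab infusion; the protocol suggests this for fatigue only. Safety reporting is descriptive, and no test, significance level or efficacy analysis is touched.

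**What to change.** In SAP 12.1.3, allocate Visit 5-day events with unknown start time to the Open-label Period unless the record, for example an investigator assessment, shows onset before the infusion. Report the number of such events by arm, with the alternative allocation as a sensitivity summary.

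Whether the eCRF can mark onset before the Visit 5 infusion is not stated in the documents. If it cannot, keep the present default and add only the count by arm and the sensitivity summary, which need no such field.

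Do not add these events to the Visit 5 day-of-dosing summary, which is defined by onset after infusion start. Footnote their number there instead.

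The cost is one sentence in 12.1.3, a matching change to the period flag, one small table and a footnote. The downside is that a few events that truly began earlier on the Visit 5 day would be counted as Open-label; the sensitivity summary shows how much that matters.
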